10.5 Change from Baseline

Change from baseline (CFB) is defined as:

post-baseline – baseline

CFB will be calculated only for patients with both a baseline and post-baseline value.

10.6 Percent Change from Baseline

Percent CFB is defined as:

$$\left(\frac{CFB}{baseline}\right) \times 100\%$$

If baseline and post baseline are averages (derived using a known numerator and denominator) percent CFB will be derived as:

 $\left(\left(\frac{\text{total post-baseline numerator } \times \text{ baseline denominator}}{\text{total baseline numerator } \times \text{ post-baseline denominator}}\right) - 1\right) \times 100\%$

Percent CFB will be calculated only for patients with both a baseline and post-baseline value.

If the baseline is zero, then percent CFB will be derived as:

 $\left(\left(\frac{\text{total post-baseline numerator}}{\text{post-baseline denominator}}\right) + 1\right) \times 100\%$

10.7 Time Conversion

Time conversion will follow the rules described below:

- 1 Week = 7 days
- 1 Month = 30.4375 days
- 1 Year = 365.25 days

10.8 Patient Disposition and Treatment Duration

The time in study expressed in days is defined as:

```
(Last Day in Study – date of randomization) + 1
```

See Section 10.1 for source of dates.

The duration of IMP exposure expressed in days will be derived as:

(IMP End Date – IMP Start Date) + 1

See Section 10.1 for source of dates.

Duration of IMP will also be categorized as follows:

- 1 to 14 days
- 15 to 28 days
- 29 to 56 days
- 57 to 84 days
- 85 to 91 days
- > 91 days

The treatment arm total duration of IMP exposure expressed in patient-years will be derived as follows:

$$\frac{\sum_{i=1}^{i=n} Di}{365.25}$$

With n being the number of patients within the treatment arm and SAF and i=1,2, 3,...,n, and, with Di being the duration of IMP exposure (in days) for patient i.

10.9 IMP Dosing – Number of Sprays Summary

For each parameter presented in this section,

- The derivation will be carried out for the titration, maintenance and on-treatment periods (as defined in Section 10.2.2)
- eDiary information will be used to retrieve the total daily number of sprays taken by a given patient
- A missing diary day is defined as any day where the eDiary is not completed.

The mean number of daily sprays a patient has taken will be calculated for each period as:

total number of sprays taken during the period

the number of non-missing diary days during the period

Based on the above the mean number of daily sprays will also be categorized as follows:

- ≤ 6 sprays per day
- 6 to \leq 12 sprays per day
- > 12 sprays per day

The modal number of sprays per patient

• refers to the most frequent number of sprays per day a patient has taken during the period.

The maximum number of sprays per patient

• refers to the maximum number of sprays a patient has taken in a single day during the period.

10.10 Compliance, Optimized Dose and Drug Accountability

Percent compliance will be derived, for each patient, during the maintenance phase (as defined in Section 10.2.2), based on optimized and amended doses information as reported in the "Dose amendment" eCRF form and the total daily number of sprays derived from the eDiary as the sum of morning and evening number sprays.

A compliant day, is defined for each patient as a day when the total number of sprays taken is

- Within ± 1 (and between 1 and 12) of the patients' optimized dose when sprays are taken outside of an amended dose period
- Equal to the amended dose ± 1 spray (and between 1 and 12) when sprays are taken between start and stop date of an amended dose period as collected in the eCRF.

The percent compliance will then be defined as:

 $100\% \times \left(\frac{\text{number of compliant days}}{\text{the number of non-missing diary days during the period}}\right)$

The percent compliance will also be categorized as follows:

- < 80%
- ≥ 80% to < 90%
- ≥ 90% to < 100%
- = 100%

The following will be derived for the titration, maintenance and on-treatment periods (as defined in Section 10.2.2):

Statistical Analysis Plan for Protocol GWSP18023 (22-MAR-2022)

The percent of "0" total daily sprays is defined at patient level as:

100% × $\left(\frac{\text{the number of days where total daily dose is 0}}{\text{the number of non-missing diary days during the period}}\right)$

The percent of " > 12" total daily sprays is defined at patient level as:

 $100\% \times \left(\frac{\text{the number of days where total daily dose is > 12}}{\text{the number of non-missing diary days during the period}}\right)$

The percent of missing diary day IMP information is defined for each patient as:

 $100\% \times \left(\frac{\text{the number of diary days missing dosing information during the period}}{\text{period duration}}\right)$

The final optimized dose is defined as:

- The last amended dose in case of any dose adjustment •
- The optimized dose if no dose adjustment .

Total IMP used (sprays) is defined as:

10.11 Age

The age at consent will be determined as follows:

- If age is recorded in the eCRF then this will be used for analysis •
- If only year of birth is known, then age is derived as: •

(date of informed consent - date of birth) + 1

365.25

where date of birth is imputed to the 30th June of the year of birth. However, if derived age is resolved to 17 years and inclusion criteria 1 is met then age will be set to 18 years.

Based on the above, age will also be categorized as: < 18, \geq 18 to < 45, \geq 45 to < 65 and \geq 65 years.

10.12 Body Mass Index

At each weight measurement, the Body Mass Index (BMI) will be derived using height collected at screening.

BMI (kg/m^2) is calculated using the following formula:

Weight (kg) (Height (cm)*0.01)2

BMI will be categorized as follows:

- < 18.5;
- ≥ 18.5 and < 25.0
- ≥ 25.0 and < 30.0;
- ≥ 30.

10.13 Disease History

As part of disease history description, the following parameters will be derived:

Time since diagnosis of multiple sclerosis (MS) (years):

(Date of Informed Consent – Date of MS diagnosis) + 1

365.25

Age at diagnosis of MS (years):

(Year of MS diagnosis - Year of Birth) + 1

Time since onset of spasticity due to MS (years):

(Date of Informed Consent – Date of Onset of Spasticity due to MS) + 1 365.25

Age at onset of spasticity due to MS (years):

(Year of Onset of Spasticity due to MS – Year of Birth) + 1

Time between MS diagnosis and onset of spasticity due to MS (years):

(Date of onset of spasticity due to MS – Date of MS diagnosis) + 1 365.25

Time between MS diagnosis and onset of spasticity due to MS (months):

(Date of onset of spasticity due to MS – Date of MS diagnosis) + 1 30.4375

The following conversion will be applied as appropriate:

- Time since last relapse (month) = Time since last relapse (year) * 12,
- Time since last relapse (month) = Time since last relapse (day) / 30.4375.

Age at diagnosis of MS and age at onset of spasticity due to MS are only using year because only year of birth is planned to be collected.

If date of MS diagnosis and/or date of onset of spasticity due to MS are unknown or partial, they will be imputed as follow:

- if only day is missing, it will be imputed to the 15th of the month,
- If day and month are missing, they will be imputed to the 30th June of the year,
- However, if any of these dates fall after the informed consent date, they will be set to the informed consent date. If, due to imputation rule the date of onset of spasticity due to MS falls before the date of MS diagnosis, it will be set to the date of MS diagnosis.

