12.2.5 Disease Characteristics

The following disease characteristics will be summarized:

Multiple sclerosis diagnosis

- MS subtype (primary progressive, secondary progressive, relapsing-remitting),
- Time since diagnosis of MS (year)
- Age at diagnosis of MS (year)
- Time since onset of spasticity due to MS (expressed in month or year as appropriate),
- Age at onset of spasticity due to MS (year)
- Time between MS diagnosis and onset of spasticity due to MS (expressed in month or year as appropriate)
- Also presenting the number and percentage of patients experiencing spasticity before MS diagnosis.
- Number of relapses in the past 12 months
- Time since last relapse (expressed in months or years as appropriate

- Expanded Disability Status Scale (EDSS) score
- Ambulatory Status

As defined in Section 10.13).

Current MS medication

The following summaries relating to current (are defined in Section 12.3.2) MS medications will be provided:

- At least 1 MS medication (y/n)
- Current use of antispasticity medication
 - Baclofen (y/n)
 - Tizanidine (y/n)
 - Dantrolene (y/n)
 - Benzodiazepine (y/n)
 - Muscle relaxants (y/n)
 - Botulinum toxin (y/n)
 - Gabapentin (y/n)
 - Pregabalin (y/n)
 - Other (y/n)
- Number of antispasticity medications
 - 0
 - 1
 - 2
- At least 1 MS disease-modifying drug (DMD) (y/n)
- Current use of medication to treat other MS Symptoms
 - Dalfampridine (y/n)
 - Fampridine (y/n)

Current MS medications are those taken at time of randomization/1st IMP dosing as described in Section 12.3.2). They will be determined based on information captured in the eCRF "Concomitant medication" form; further determination criteria being given in Appendix 8.

Prior use of cannabis or cannabinoid products

At Screening (Visit 1), any intermittent or regular previous use of cannabis or cannabinoid products for medical or recreational purposes will be recorded on the Prior Cannabis Use CRF form.

Prior use of cannabis or cannabinoid products will be summarized for the following

- Prior use of cannabis or cannabinoid products (PUC) (y/n)
 - For PUC = Y: Medicinal use (y/n)
 - For PUC = Y: Recreational use (y/n)

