7.0 Statistical Methods

The abbreviated reporting will follow the strategy as detailed in **Table 7-1**. Although the study will terminate early, the primary hypothesis will still be tested as per the final SAP.

Addendum to Statistical Analysis Plan for Protocol GWSP18023 (17-FEB-2023)

Table 7-1 Strategy for abbreviated reporting

Hierarchy	Strategy	Endpoint	Relevant Sections of SAP V1.0 to be Used
Primary & C Secondary Efficacy s Endpoints ((n	Conduct primary inferential analysis, standard descriptive statistics and listing. Sensitivity and supplemental (including subgroup analyses) will not be conducted. Figures will not be produced.	Daily spasm count	12.5.2.1 & 12.5.2.4
		MSSS-88	12.5.3.1 & 12.5.3.4
Secondary Safety Endpoints (excluding PK)	As described in SAP with the exception of figures, subgroup summaries, repeats on FAS.and those specific to an endpoint (detailed in final column).	TEAEs Clinical laboratory tests	 12.8.1 & 12.8.2 Excluding the following summaries: by time of first onset by AE duration of TEAEs related to IMP by maximum severity of TEAEs related to IMP and leading to IMP discontinuation by maximum severity of serious TEAEs related to IMP 12.8.3 Excluding the following summaries: Values outside of normal ranges Shift tables based on CTCAE v5.0 grade Shift tables based on normal range indicator will be presented by visit rather than by most extreme value and last
		Vital signs	on-treatment value.
		FCG	12.0.7
		C-SSRS	12.8.5.3
Secondary Safety Endpoints (PK)	No processing, analyses or reporting	PK	NA

Addendum to Statistical Analysis Plan for Protocol GWSP18023 (17-FEB-2023)

Exploratory	Listings only, no descriptive or	MSSS-88 subscales	12.5.3.4
Endpoints	inferential statistics or figures.	NRS spasm severity	12.5.4.2
		NRS spasticity	12.5.4.3
		T25FW	12.5.4.4
		SF-36	12.6.1
Other data	As described in SAP with the	Disposition	12.1
e s tł	exception of figures, subgroup summaries, repeats on FAS and those specific to a section (detailed in final column).	Demographics	12.2.1
		Disease Characteristics	12.2.5
		Medical History	12.2.4
		Prior and Concomitant	12.3.2
		Medications and	Excluding summaries of post-treatment medications
		Therapy	
		Treatment Exposure	12.3.1
		Protocol deviations	12.4
			Excluding summaries of major IPDs
		Other Safety	12.8.5.1, 12.8.5.4, 12.8.5.5, 12.8.5.6, 12.8.5.7
		Monitoring of Drug	12.8.6
		Abuse Liability	Excluding the summary of triggered events
	1		

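### SAP 10.13 adds a whole year to age at MS diagnosis and age at spasticity onset, so two descriptive rows run about one year high, equally in both arms

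*SAP*

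**What the plan says.** SAP 10.13 (Disease History) gives two formulas, both labelled in years:

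- Age at diagnosis of MS: "Year of MS diagnosis - Year of Birth) + 1"
- Age at onset of spasticity: "Year of Onset of Spasticity due to MS – Year of Birth) + 1"

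The section explains the use of calendar years by saying that the two ages "are only using year because only year of birth is planned to be collected". It gives no reason for adding 1.

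The time-since variables in the same section work in days. Time since diagnosis, for example, has the numerator "Date of Informed Consent – Date of MS diagnosis) + 1" and is divided by 365.25.

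SAP 10.11 derives age at consent differently. An age recorded in the eCRF is used if there is one. If only the year of birth is known, age is a day count divided by 365.25, "where date of birth is imputed to the 30th June of the year of birth".

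SAP 12.2.5 lists both ages for summary ("Age at diagnosis of MS (year" and "Age at onset of spasticity due to MS (year"). Table 7-1 of the addendum, written after the decision to stop the study early, keeps the "Disease Characteristics" output by reference to SAP 12.2.5.

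**The concern.** Adding 1 to a difference between two dates is the usual way to count days inclusively. Applied to a difference between two calendar years it has no such meaning. It moves every patient's age up by a year, and the year-only data do not call for it. With only the two years known, D - B is already centred on exact age.

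Age at diagnosis and age at onset are basic descriptors of the trial population. Their mean, median, quartiles, minimum and maximum would all be reported too high, in a summary that survives the abbreviated reporting. They would also be systematically out of line with what the SAP's own age and time-since-diagnosis rules imply.

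**Working it through.** The plan states no numerical result that depends on these formulas, so there is no figure to reproduce. The check takes the formulas as written and compares them with true age. Let B be the year of birth and D the year of the event.

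**1. Unit of the added 1.** In the day-based formulas it is worth 1/365.25 = 0.003 year. In the two age formulas it is worth 1 year.

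**2. Bound on true age.** The oldest a patient can be at the event is when birth falls on 1 January of B and the event on 31 December of D. That age is D - B + 1 years less one day. Exact age is therefore below D - B + 1 for every pair of dates. Completed age is D - B if the birthday has been reached and D - B - 1 if not, so the formula exceeds it by 1 or 2. For example, a patient born in 1980 and diagnosed in 2010 was 29 or 30. The formula gives 2010 - 1980 + 1 = 31.

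**3. Size.** All 365 × 365 = 133,225 combinations of birth day in 1975 and diagnosis day in 2010 were enumerated. The formula gives 2010 - 1975 + 1 = 36 throughout.

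| Error against | Formula as written | Without the + 1 |
|---|---|---|
| Exact age (days/365.25) | min +0.003, mean +1.00, max +2.00 | min -1.00, mean 0.00, max +1.00 |
| Completed years | +1 in 66,795 (50.1%), +2 in 66,430 (49.9%); mean +1.50 | 0 in 50.1%, +1 in 49.9%; mean +0.50 |
| Age from a 30 June birth date (SAP 10.11 fallback) | +0.49 to +1.49, mean +0.99 | -0.51 to +0.49, mean -0.01 |

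The right-hand cell of the last row is the left-hand cell minus 1.

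**4. Consistency with the SAP's other rules.** Take a patient with birth year 1975, diagnosed 15 June 2010, who consented on 15 June 2021.

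- Age at consent (30 June rule): 16,788/365.25 = 45.96
- Time since diagnosis: 4,019/365.25 = 11.00
- Implied age at diagnosis: 45.96 - 11.00 = 34.96
- SAP 10.13: 2010 - 1975 + 1 = 36, which is 1.04 higher
- Without the + 1: 35, which is 0.04 higher

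**5. An extreme but eligible case.** Protocol 6.1 requires MS to have been diagnosed at least 12 months before Visit 1. Take birth year 1980, diagnosis on 15 January 2021 and consent on 1 March 2022. Age at consent by the 30 June rule is 15,220/365.25 = 41.67, and time since diagnosis is 411/365.25 = 1.13 years. SAP 10.13 gives age at diagnosis as 2021 - 1980 + 1 = 42, above the age at consent. Without the + 1 it gives 41.

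**The case against.** The strongest reply is that very little depends on these values. Both ages are descriptive. They are not among the covariates in SAP 9.2 or the subgroup factors in SAP 9.3, and they feed no endpoint or test. The same constant is added for every patient, so it cannot create or hide an imbalance between arms. It leaves the standard deviations and the gap between the two ages unchanged. All of this stands, and it sets the ceiling on the importance of the point.

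A second reply is that year-level data cannot give an exact age anyway. That is true, but it explains the spread around the true value and not a shift in one direction. Reading the result as the patient's Nth year of life does not help either. The label is age in years, and the formula equals completed age plus 1 in only about half of cases.

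A reader might infer three stronger things that the documents do not support:

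- **That the whole disease-characteristics table is wrong.** Only two rows are affected. MS subtype, the time-since variables, relapses, EDSS, ambulatory status and medications do not use these formulas.
- **That the two ages will clash with an age row beside them.** Age at consent is summarized under demographics (SAP 12.2.1), which the addendum lists separately. Some patient-level disagreement would remain even after correction, because year-only subtraction is imprecise. The valid complaint is systematic bias.
- **That ages above the age at consent will be common.** The case in step 5 is possible, but the documents give no frequency of diagnosis or onset so close to consent.

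**Conclusion.** The point holds. That every derived value exceeds true age follows from the calendar alone and needs no assumption. So does the excess of 1 or 2 over completed years. The averages (+1.0 year against exact age, +1.5 against completed years) assume birth and event dates spread uniformly within the year. Nothing elsewhere in the SAP or the addendum corrects the formulas.

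The consequence is limited to two descriptive rows of the SAP 12.2.5 summary, shifted upward equally in both arms. It is a minor error, but the reported numbers will be wrong if the rule is programmed as written.

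**What to change.** Delete the + 1 from both age formulas in SAP 10.13 and from the ADaM specification, leaving year of event minus year of birth. This is a small edit to two derivations. It needs no new data and does not depend on treatment allocation. A table footnote should say that the ages come from calendar years only, since an individual value can still differ from exact age by up to 1 year and is 1 above completed age in about half of cases.

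Subtracting time since the event from age at consent may look like a neater solution, but it is not recommended. SAP 10.11 takes the eCRF-recorded age first, and the documents do not say whether that age is in completed years. If it is, the result would run about half a year low on average. Mixing recorded and derived ages would make the bias vary between patients.

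A related matter to reconcile at the same time: Protocol 9.2.3 lists date of birth among the screening data, as local rules allow, while SAP 10.13 expects only the year. This does not change the case for removing the + 1.

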10.14 Renal Function Formula

Estimated Glomerular filtration rate (eGFR) (mL/min/1.73m²) will be categorized as follows:

- \geq 90 as normal renal function,
- ≥60 and < 90 as mild renal impairment,
- ≥30 and < 60 as moderate renal impairment,
- ≥15 and < 30 as severe renal impairment,
- <15 as end stage kidney failure.

10.16 Mobile Health Platform Data Handling

Data downloaded from the Mobile Health platform (MHP) such as number of morning and evening sprays administered, NRS scales, number of spasm counts, C-SSRS questionnaire, MSSS-88 questionnaire, have specific information to link the date of MHP data to the date it is referring to which is to be reported in SDTM and ADaM as detailed in Table 10.16-1. In general, any time the variable XPGRPID contains the term "Late" the date to be used refers to the day before the one coming from MHP.

An exception to this is data collected under the 'Initial late' prompt prior to December 2nd 2021 when the incorrect prompt "Enter the number of spasms you had since bedtime yesterday until now." was given. Data collected under the Initial late diary (ie where variable XPTESTCD end in _117) using this prompt will not be included in the analysis. Data collected under the Initial late diary using the prompt "Enter the number of spasms you had in the 24 hours before your bedtime yesterday." will be included.

XPGRPID	Explanation
Initial on time Diary	Served from 6:00pm to 11:59 pm on the day a participant is moved to screening
Initial late Diary	Served from 12:00 am to 3:00 pm the next day when the initial On Time Diary was NOT completed the previous day
On time diary	Served from 6:00pm to 11:59 pm when the Initial On Time, On time, or Missed On Time Diary was completed the previous day
Late diary	Served from 12:00 am to 3:00 pm when On Time Diary was NOT completed the previous day
Missed on time	Served from 6:00pm to 11:59 pm when an Initial Late, or Missed Late Diary was served on the same day
Missed late	Served from 12:00 am to 3:00 pm when the Missed On Time Diary was Not completed the previous day

Table 10.16-1 MHP data - Date Handling

10.17 Daily Spasm Count

The spasm count is recorded daily via the eDiary. The average daily spasm count will be derived for each patient for the following periods: in the baseline period, the three 4-week periods in the randomized period (Week 1 to 4, Week 5 to 8 and Week 9 to 12), the follow-up baseline period and the follow-up period (definitions for the periods and baseline are described in Section 10.2.2 and Section 10.4.1).

The average daily spasm count for each period is defined as follows:

Total spasm count for the period Number of days in which the daily diary was completed during the period

The average daily spasm count value will be set to missing under the following conditions:

- if less (<) than 15 days with non-missing data and more than or equal to (≥) 10 consecutive days with missing data for the three 4-week periods in the randomized period.
- if less (<) than 7 days with non-missing data and more than or equal to (≥) 5 consecutive days with missing data for the follow-up period.

The change from baseline will be calculated (as described in Section 10.5) for the three 4-week periods in the randomized period and the follow-up period.

The percent change from baseline will be calculated (as described in Section 10.6) for the three 4-week periods in the randomized period.

The percentage change from baseline values for the Week 9 to 12 period will be categorized using the following responder analysis cut-offs:

- 20% improvement (≤ -20% vs > -20%)
- 30% improvement (≤ -30% vs > -30%)
- 40% improvement (≤ -40% vs > -40%)
- 50% improvement (≤ -50% vs > -50%).

Missing average daily spasm count will be considered as not having met any of the improvement criteria (imputed as failure) for the responder analysis.

On-treatment average daily spasm count will be derived for each patient for the three 4-week periods in the randomized period using the same derivation as for average daily spasm count detailed above but using only diary records before the IMP End Date. The same criteria for missing data will be applied.

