Patients are eligible for randomization in the trial if, in addition to continuing to meet the Screening (Visit 1) inclusion criteria, they also meet ALL of the following criteria during the first 28 days of the baseline period. (Note: patients are expected to start completing their electronic diary in the evening of their screening visit):

- 11. In the opinion of the investigator, the patient is able to interpret and report spasm count data accurately
- 12. Completed their electronic diary for at least 25 of the first 28 days of the baseline period
- 13. Has an average daily spasm count of  $\geq$  4 during the first 28 days of the baseline period, as recorded by the patient
- 14. Has no more than 35 spasms on any single day of the first 28 days of the baseline period, as recorded by the patient
- 15. Does not have > 7 consecutive days without experiencing any spasm during the first 28 days of the baseline period

If, for any reason, the patient is unable to attend the site for randomization within the visit window, the site should contact the Medical Monitor or the sponsor to discuss.

In addition to meeting the Screening (Visit 1) inclusion criteria and additional inclusion criteria 11 to 14, any patient with more than 28 days between Visit 1 and Visit 2 would need to meet ALL of the following criteria prior to randomization:

- 16. Completed their electronic diary for at least 85% of days between Visit 1 and Visit 2
- 17. Has an average daily spasm count of  $\geq$  4 between Visit 1 and Visit 2 (randomization), as recorded by the patient
- 18. Has no more than 35 spasms on any single day between Visit 1 and Visit 2, as recorded by the patient
- 19. Does not have > 7 consecutive days without experiencing any spasm between Visit 1 and Visit 2

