# 13.6.1 Primary Endpoint

The primary endpoint is the change from baseline in average daily spasm count (the average daily spasm count from Days 57 to 84 compared to the average daily spasm count for the baseline period) for all randomized patients regardless of treatment compliance.

The average daily spasm count will be calculated for the baseline period and each 28-day period corresponding to Days 1 to 28, Days 29 to 56, and Days 57 to 84. The change from baseline for average daily spasm count will be calculated for Days 1 to 28, Days 29 to 56, and Days 57 to 84.

Average daily spasm count for each period is defined as follows:

Total spasm count for the period Number of days in which the daily diary was completed during the period

For post-randomization data, the average daily spasm count over the 28-day period will only be calculated if there are  $\geq 15$  days of non-missing data and < 10 consecutive days of missing data. If there are < 15 days of non-missing data or  $\geq 10$  consecutive days of missing data then the average daily spasm count for the 28-day period will be set to missing.

The average daily spasm count and change from baseline will be summarized by treatment for each 28-day period.

The change from baseline will be analyzed using mixed model repeated measures (MMRM), using data for each 28-day period. The model will include baseline average daily spasm count, prior cannabis use, region (US versus non-US), period, treatment arm,

period by treatment arm interaction, and period by baseline interaction as fixed effects. Period repeated within each patient will be included as a repeated effect. Denominator degrees of freedom adjustment will be performed using the Kenward-Roger method.

The within-patient correlation structure will be modelled using an unstructured covariance matrix. If the model does not converge the following structures will be used in order of preference Toeplitz, first-order autoregressive and Compound symmetry.

The least squares mean estimates for each treatment arm and period, along with the standard error and 95% confidence intervals (CIs), will be presented. In addition, estimates of the treatment difference at each period in change from baseline will be presented along with standard errors of the difference and 95% CIs. The primary comparison is the estimate of the treatment difference for the Days 57 to 84 period.

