# 13.6.3 Exploratory Endpoints

The exploratory endpoints are as follows:

- Change from baseline in the 8 subscale scores of the MSSS-88 at Visit 6
- Change from baseline in average daily 11-point NRS spasm severity score to Days 57 to 84
- Change from the last 7 days of baseline in average daily 11-point NRS spasticity score to Days 78 to 84
- Change from baseline in the SF-36 total score at Visit 6 (Day 85)
- Change from baseline in T25FW (measured in seconds) test at Visit 6 (Day 85)

The NRS and MSSS-88 endpoints will be analyzed using the methods used for the primary endpoint described in Section 13.6.1 and secondary endpoints described in Section 13.6.2, respectively.

The T25FW and SF-36 endpoints will be analyzed using analysis of covariance models with baseline as a covariate and treatment, prior cannabis use and region (US versus non-US) effects.

Each endpoint will be summarized by treatment arm and visit/period.

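### The SAP joins the primary endpoint's two missing-diary conditions with AND where the protocol joins them with OR, so the primary MMRM would keep period averages that the protocol sets to missing

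*SAP*

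**What the plan says.** Protocol 13.6.1 states the rule for post-randomization 28-day averages in both directions. The average is calculated only with at least 15 "days of non-missing data and < 10 consecutive days of missing data". The complement follows: "If there are < 15 days of non-missing data or $\geq 10$ consecutive days of missing data", the average is set to missing. The two statements agree.

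SAP 10.17 sets the average for each of the three 4-week periods to missing "if less (<) than 15 days with non-missing data and more than or equal to (≥) 10 consecutive days with missing data". The thresholds are the protocol's; the connector is not.

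The rule feeds the primary analysis directly. SAP 12.5.2 takes the primary endpoint from 10.17, and 12.5.2.1 enters every available post-baseline period average from the FAS into the MMRM. SAP 6.2 reports no changes from the protocol. After early termination, addendum section 7.0 states that "the primary hypothesis will still be tested as per the final SAP" and does not touch 10.17.

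SAP 10.19 repeats the AND wording for NRS spasm severity, although protocol 13.6.3 says "The NRS and MSSS-88 endpoints will be analyzed using the methods used for the primary endpoint described in Section 13.6.1". AND also appears in 10.20 (NRS spasticity) and in the follow-up bullets of 10.17 and 10.19, where the protocol gives no thresholds.

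**The concern.** The two documents give incompatible rules for whether a patient has a Days 57 to 84 value, which is the primary comparison. Negating a rule of the form A and B gives not-A or not-B. The SAP appears to have negated both halves and kept the connector, which looks like a drafting slip. Because 6.2 declares nothing, a reader cannot tell whether the looser rule was intended.

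A programmer following the SAP literally would analyse averages that the protocol treats as missing and leaves to the MMRM. One who reads the bullet as two separate triggers would produce a different primary dataset from the same text. If the conflict surfaces only after unblinding, the choice between the rules would be made with results visible.

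**Working it through.** The plan gives no figure for this rule. The sample size of 446 does not depend on it.

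**Logic.** Let d be the number of completed diary days out of 28 and g the longest run of missing days.

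- Protocol: keep if d ≥ 15 and g < 10; otherwise missing.
- SAP: missing only if d < 15 and g ≥ 10; otherwise keep.

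Every period missing under the SAP is also missing under the protocol, so the SAP can only keep more. The rules differ when exactly one condition fails.

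1. d ≥ 15 and g ≥ 10. A gap of at least 10 leaves d ≤ 28 − 10 = 18, and d ≥ 15 leaves g ≤ 28 − 15 = 13. This gives 15 to 18 diary days with a gap of 10 to 13.
2. d ≤ 14 and g ≤ 9. The 28 − d missing days fall into at most d + 1 gaps of at most 9 days, so 28 − d ≤ 9(d + 1), which gives d ≥ 1.9. This gives 2 to 14 diary days. Two is an extreme bound: only 3 of the 378 two-day patterns qualify.

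**Scattered missingness.** The documents give no post-randomization completion rate, so completion is assumed independent from day to day with probability p. An exact recursion over the 28 days (tracking days completed, current gap and longest gap, without simulation) gives the share of periods kept only by the SAP:

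| p | Share kept only by the SAP |
|---|---|
| 0.90 | 0.00001% |
| 0.85 | 0.001% |
| 0.80 | 0.04% |
| 0.75 | 0.4% |
| 0.70 | 2.1% |
| 0.65 | 7.3% |
| 0.60 | 18.6% |
| 0.50 | 56.5% |

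The p = 0.50 row can be checked by counting. Of 2^28 = 268,435,456 patterns, the protocol sets 154,292,028 to missing and the SAP 2,602,624. The difference is 151,689,404, or 56.5% (16,000 patterns of type 1 and 151,673,404 of type 2).

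For scale, at p = 0.80 and the planned 446 patients the expected number of affected Days 57 to 84 values is 446 × 0.00037 = 0.17. At p = 0.70 it is 446 × 0.0207 = 9.2. The only completion figure in the documents is the entry criterion, "Completed their electronic diary for at least 25 of the first 28 days of the baseline period", which is 25/28 = 89%.

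**Diary that stops mid-window.** Day 57 is window day 1, so a last entry on Day 71, 72, 73 or 74 is window day j = 15, 16, 17 or 18, with a final gap of 28 − j = 13, 12, 11 or 10. The gap condition fails, so status switches if d ≥ 15. If each of the j − 1 earlier days is completed independently with probability q (assumption), the chance of switching is P(Binomial(j − 1, q) ≥ 14). For Day 71 this is q^14, for example 0.90^14 = 0.229.

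| Last entry | q = 1 | q = 0.95 | q = 0.90 |
|---|---|---|---|
| Day 71 | 100% | 49% | 23% |
| Day 72 | 100% | 83% | 55% |
| Day 73 | 100% | 96% | 79% |
| Day 74 | 100% | 99% | 92% |

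Stopping by Day 70 leaves at most 14 diary days and a gap of at least 14, which is missing under both rules. Stopping on Day 75 with a complete diary leaves 19 days and a gap of 9, which is kept under both.

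**The case against.** Four points can be made for the SAP.

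- **Size.** If completion stays near the entry level, scattered missingness changes almost nothing, and only a narrow band of diary stoppers switches. The rows at 65% and below have no basis in the documents. This stands, and those rows should be read only as the far end of a range.
- **The looser rule is not shown to be worse.** It only adds observed data, the treatment-policy estimand uses all observed values, and the protocol leaves further missing-data detail to the SAP. This stands as far as it goes: no bias has been demonstrated. But adding detail does not cover reversing a stated rule, and an intended change belongs in 6.2.
- **The addendum is not the cause.** Its Table 7-1 says "Sensitivity and supplemental (including subgroup analyses) will not be conducted", but none of the dropped analyses varied this rule, and the period summaries and patient listing remain. This is right. With or without the addendum, no planned inferential analysis would show whether the rule matters.
- **Wording elsewhere in the SAP.** Table 12.4-2, row 03, joins the same thresholds with and/or for a baseline-diary deviation. It does not govern post-randomization periods. It supports a slip over a deliberate choice.

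The NRS and follow-up items are secondary. The protocol's explicit thresholds cover spasm count, and the addendum reduces the NRS data to listings and drops the follow-up analysis.

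**Conclusion.** The concern holds. SAP 10.17 contradicts protocol 13.6.1 on the derivation of the primary endpoint; the difference is undeclared and the addendum does not repair it. The two sets of periods kept only by the SAP follow from the rules without assumptions, and in the extreme an average could rest on 2 diary days against the protocol's minimum of 15.

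The practical size rests on a completion rate that the documents do not give and on the assumption of independent days: negligible at 85% or above, about 2% of periods at 70%, and concentrated in patients whose diary stops between Days 71 and 74. The direction of bias and the effect on power cannot be computed from the documents. The case for correction is that the primary endpoint of a confirmatory trial has two incompatible prespecified rules, not that a large effect is predicted.

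**What to change.** Before unblinding, use the addendum to replace the connector between the two conditions with OR in the SAP 10.17 bullet for the three 4-week periods. The on-treatment average inherits the corrected rule. Make the same change in the matching 10.19 bullet. If AND is intended, list it in SAP 6.2 as a change from the protocol, with a reason. Check 10.20 and the follow-up bullets for the same slip; the protocol sets no thresholds there, so they are points to confirm and not contradictions.

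The cost is one word in each of two sections. The sample size does not change. If diary completion is near the entry level, few patient-periods change status, and those that become missing are handled by the planned MMRM.
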